Participants will be treated for up to 10 days. Those participants who have demonstrated clinical improvement may be considered for a shorter treatment period.

Screening is to be completed within 2 days prior to the Day 1 visit.

At the screening visit and all subsequent study visits (or until hospital discharge - whichever comes first) laboratory analyses (hematology, chemistry, inflammatory markers, urinalysis, and routine coagulation test), vital signs (heart rate, temperature, blood pressure [mean arterial pressure if available, systolic and diastolic], respiratory rate [if not on a ventilator], oxygen saturation), complete or symptom-directed physical examinations will be performed. Nasopharyngeal and oropharyngeal samples (combined) OR nasal and oropharyngeal samples (combined), and rectal or fecal swab will be collected on Days 1, 3, 5, 7, and 10 (if feasible) for SARS-CoV-2 reverse transcriptase quantitative polymerase chain reaction (RT-qPCR) viral load testing and possible viral resistance testing. Endotracheal tube aspirates will also be collected if the participant is intubated. If the participant is discharged prior to Day 10, the samples for SARS-CoV-2 RTqPCR viral load testing and possible viral resistance testing and possible viral resistance testing can be collected by assigned study staff at the participant's home or as an outpatient on the assigned days noted above, if feasible. Serum for SARS-CoV-2 IgG, IgM, and IgA serology will be collected at Screening, Day 5, Day 10 (if feasible), and the Day 30 Follow-up visit (for participants weighing ≥ 12 kg).

Clinical scoring using PEWS and the Ordinal Scale will occur at Screening and daily through the duration of dosing.

Adverse events and concomitant medications will be assessed from Screening through the Day 30 Follow-up visit.

As many of the specified sparse PK assessments should be obtained from each participant as is feasible.

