Day 7	SARS-CoV-2 RT-qPCR viral load	7	6	8
Day 10	SARS-CoV-2 RT-qPCR viral load	10	9	11
Discharge*	SARS-CoV-2 RT-qPCR viral load	Day of discharge		

* If the participant is discharged prior to Day 10, the SARS-CoV-2 samples/swabs will be collected on the day of discharge. Thereafter, these samples can be collected by assigned study staff at the participant's home or as an outpatient on the assigned days noted above.

Table 3-4.	Analysis Windows	for Serology for SAR	S-CoV-2 (IgG, IgM, and IgA)
	•		

Visit ID	Testing	Nominal Day	Lower Limit	Upper Limit
Baseline/Day 1#	Serology for SARS-CoV-2 (IgG, IgM, and IgA)	1		1 (pre-dose)
Day 5	Serology for SARS-CoV-2 (IgG, IgM, and IgA)	5	4	6
Day 10	Serology for SARS-CoV-2 (IgG, IgM, and IgA)	10	9	11
Discharge*	Serology for SARS-CoV-2 (IgG, IgM, and IgA)	Day of discharge		
Day 30	Serology for SARS-CoV-2 (IgG, IgM, and IgA)	30	25	35

Includes the serum for SARS-CoV-2 IgG, IgM, and IgA serology collected at Screening.

* If the participant is discharged prior to Day 10, the serology for SARS-CoV-2 will be collected on the day of discharge. Thereafter, these samples can be collected by assigned study staff at the participant's home or as an outpatient on the assigned days noted above.

Clinical scoring using the PEWS (0 to 3 on each of 3 categories) will be recorded at Screening and daily through the duration of dosing. Results will be summarized for each Study Day without windows.

The 7-point Ordinal Scale is an assessment of the clinical status of a given Study day. Each day, the worst (ie, lowest ordinal) score from the previous day will be recorded (ie, on Day 3, the

lowest ordinal score from Day 2 is obtained and recorded for Day 2). Results will be summarized for each Study Day without windows.

3.8.3. Selection of Data in the Event of Multiple Records in an Analysis Visit Window

Depending on the statistical analysis method, single values may be required for each Study Day or analysis window. For example, change from baseline by visit usually requires a single value, whereas a time-to-event analysis does not require 1 value per Study Day or analysis window.

If multiple valid, nonmissing measurements exist for a Study Day/analysis window, records will be chosen based on the following rules if a single value is needed:

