As oxygen support status will be collected only while the participant is in the hospital, if a participant is discharged alive and dies afterwards, the participant will be included only in the summary for participants discharged alive.

Change from baseline in SARS-CoV-2 viral load up to Day 10 or up to the first confirmed negative PCR result (whichever comes first)

Descriptive statistics for viral load and change from baseline in viral load will be provided by cohort and overall total for the following:

- Day of discharge and each study day up to Day 10 or up to the first confirmed negative PCR result (whichever comes first)
- Day of discharge and each study day up to Day 10

Separate summary tables will be provided for each sample type: (a) nasal/oropharyngeal samples, (b) nasopharyngeal/oropharyngeal samples, (c) endotracheal tube (ET) aspirates, and (d) rectal or fecal swabs.

Days to the first confirmed negative PCR result, where confirmed is defined by 2 consecutive negative PCR results

For each cohort and overall total, the number and percentage of participants with:

- At least 1 negative PCR result
- Confirmed negative PCR result

will be summarized separately for each sample type: (a) nasal/oropharyngeal samples, (b) nasopharyngeal/oropharyngeal samples, (c) ET aspirates, and (d) rectal or fecal swabs.

Time to first confirmed negative PCR result will be modelled separately for each sample type: (a) nasal/oropharyngeal samples, (b) nasopharyngeal/oropharyngeal samples, (c) ET aspirates, and (d) rectal or fecal swabs, using a competing risk analysis. The competing event is death. Participants not not achieving a confirmed negative PCR at the last assessment will be censored on the day of the last clinical assessment.

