12. APPENDICES

Appendix 1.Study Procedures Table

					Adı	ninistratio	n Period ^ь					Follow-up Period
	Screening	Baseline/ Day 1ª	Day 2	Day 3	Day 4	Day 5	Day 6	Day 7	Day 8	Day 9	Day 10	Day 30 (± 5 days)
Assent/Parent or Legal Guardian consent	Х											
Inclusion/Exclusion criteria	Х											
Focused medical history	Х											
Documentation of SARS-CoV-2 confirmation by PCR	Х											
ECG	Х											
Complete or symptom-directed physical examination	Х	X	X	X	X	Х	Х	X	Х	Х	Х	X
Body weight ^c	Х	Х	X	Х	X	Х	Х	X	Х	Х	Х	X
Height/Length	Х											Xd
Head circumference and last recorded Apgar score if < 24 hours of age	Х											X ^d
Birth weight and gestational age if < 56 days	х											
Vital signs (heart rate, temperature, blood pressure [MAP if available, systolic and diastolic], respiratory rate, oxygen saturation)	Х	Х	x	X	х	Х	X	x	Х	Х	х	X
Documented respiratory status	Х	X	X	X	X	Х	Х	X	Х	Х	Х	X

			Administration Period ^b							Follow-up Period		
	Screening	Baseline/ Day 1ª	Day 2	Day 3	Day 4	Day 5	Day 6	Day 7	Day 8	Day 9	Day 10	Day 30 (± 5 days)
If available, record chest radiographic impression (or other imaging) but not mandatory to perform otherwise	Х	Х	х	Х	Х	Х	Х	x	Х	х	х	
Tanner Stage assessment if ≥ 6 years of age		Х										
Hematology, chemistry, urinalysis	Х		X			Х			Х		Х	Xe
Routine coagulation test (Days 5 and 10 only for Cohorts 5-6 and Day 10 only for Cohort 7)	Х		X			Х			Х		Х	
Inflammatory Markers (D-dimer, Ferritin, qCRP, Procalcitonin, and IL-6)	Х		X			Х			Х		Х	
ESR If ≥4 kg (Cohorts 1-4 only)	Х		X			Х			Х		Х	
Neonatal bilirubin panel for all neonates < 14 days, and any neonate presenting with jaundice	Х										Х	
Serology for SARS-CoV-2 if $\geq 12 \text{ kg} (\text{IgG, IgM, and IgA})^{f}$	X					Х					X	X
Pregnancy test (urine/blood)	Х											

			Administration Period ^b							Follow-up Period		
	Screening	Baseline/ Day 1ª	Day 2	Day 3	Day 4	Day 5	Day 6	Day 7	Day 8	Day 9	Day 10	Day 30 (± 5 days)
Nasopharyngeal and oropharyngeal samples (combined), rectal or fecal swab, and ET aspirates (if intubated) for SARS-CoV-2 PCR testing and possible viral sequencing ^f		Х		X		Х		X			Х	
Pediatric Early Warning Score Improvement Scale ^g	Х	Х	X	X	Х	Х	Х	X	Х	Х	Х	
Ordinal Scale	Х	X	X	X	X	Х	X	X	Х	X	X	
Plasma PK assessmentsh			X	X		X						
IV RDV administration		Xi	Xj	Xj	Xj	Xj	Xj	Xj	Xj	Xj	Xj	
Concomitant medications	Х	X	X	X	X	Х	X	X	Х	X	X	X
Adverse events ^k	Х	X	X	X	X	Х	X	X	Х	X	X	X

CCI

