CoV = coronavirus; CRP = C-reactive protein; ECG = electrocardiogram; ET = endotracheal tube; Ig = immunoglobulin; IV = intravenous; MAP = mean arterial pressure; PK = pharmacokinetic; RDV = remdesivir (GS-5734TM); SARS = severe acute respiratory syndrome; TBD = to be determined

a If the Screening and Day 1 visits occur within 24 hours, only the following procedures need to be completed: Tanner Stage assessment and samples for SARS-CoV-2 PCR testing and viral sequencing

- b The following evaluations are to be completed on Days 2-10 or until discharge, whichever comes earlier.
- c CCI

d Record length and head circumference if < 28 days at enrollment.

e Comprehensive metabolic panel (Chemistry 14) only.

f If the subject is discharged prior to Day 10, the Serology for SARS-CoV-2 and SARS-CoV-2 samples/swabs will be collected on the day of discharge. Thereafter, these samples can be collected by assigned study staff at the subject's home or as an outpatient on the assigned days noted above.

g If a subject is on a ventilator, a score of 3 should be given in the respiratory category.

h CCI

i IV administration on Day 1 with either IV RDV 200 mg (Cohort 1), IV RDV 5 mg/kg (Cohorts 2-5), or RDV dose TBD (Cohorts 6-7).

j IV administration daily up to Day 10 with either IV RDV 100 mg (Cohort 1), IV RDV 2.5 mg/kg (Cohorts 2-5), or RDV dose TBD (Cohorts 6-7).

k All subjects presenting with multisystem inflammatory syndrome in children (MIS-C; https://emergency.cdc.gov/han/2020/han00432.asp) should be monitored and treated as clinically indicated.

CCI 1

Version 1.0

	0	1	2	3
Behavior	Playing Appropriate	Sleeping	Irritable	Lethargic and/or Confused and/or Reduced response to pain
Cardiovascular	Within normal parameters for age Pink and/or Capillary refill 1-2 seconds	Tachycardia < 20 above normal for age and/or Pale and/or Capillary refill 3 seconds	Tachycardia 20-29 above normal for age Gray and/or Capillary refill 4 seconds	Tachycardia ≥ 30 above or bradycardia ≥ 10 below normal for age or Gray Capillary refill ≥ 5 seconds
Respiratory	Within normal parameters No retractions	Respiratory rate > 10 above normal parameters using accessory muscles and/or 30+ %FiO ₂ or 3+ L/min	Respiratory rate > 20 above normal parameters and retractions and/or 40+ %FiO ₂ or 6+ L/min	Respiratory rate ≥ 5 below normal parameters with retractions and grunting and/or 50% FiO ₂ or 8+ L/min

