- Time to ≥ 2 point improvement and time to ≥ 1 point improvement: if a participant did not experience the event of interest and did not die, the participant was censored at the last non-missing assessment date. Participants who died were considered to have experienced a competing event.
- Time to recovery: Participants not achieving recovery at the last assessment were censored on the day of the last assessment. Participants who died were considered to have experienced a competing event.
- Time to discharge from hospital: Participants not discharge at the last assessment were censored on the day of the last clinical assessment. Participants who died were considered to have experienced a competing event.

18) Details on the LOQ and LOD for the viral load samples are provided below.

Table 13-3.Viral Load Sample Details

Sample type	Limit of quantitation (copies/mL)	Limit of detection (copies/mL)
Nasal/oropharyngeal samples Nasopharyngeal/oropharyngeal samples ET aspirates	1018	925
Rectal or fecal swabs	488	306

- 19) Quantitative and categorical summary on SARS-CoV2 results and change from baseline in SARS-CoV-2 viral load up to Day 10 or up to the first confirmed negative PCR result (whichever comes first)
 - For quantitative summary (e.g., mean viral load, change from baseline etc.), "Inconclusive" SARS-CoV2 result is set to missing
 - For categorical SARS-CoV2 summary, 3 categories will be included, i.e. Positive, Inconclusive, Negative
 - Positive = Any numeric result or "< 1018cp/mL SARS-CoV-2 detected" (for Nasal/oropharyngeal samples, Nasopharyngeal/oropharyngeal samples, or ET aspirates) or "< 488cp/mL SARS-CoV-2 detected" (for rectal or fecal swabs)
 - Negative = "No SARS-CoV2 detected"
 - Inconclusive = "Inconclusive"

20) Days to the first confirmed negative PCR result

- Categorical SARS-CoV2 and SARS-CoV2 negative summary will be separated out by sample type. There will be no combined positive or negative category using 2 or 3 sample types.
- Confirmed negative PCR result is defined as 2 consecutive negative results, or negative at last available sample for participants who completed or discontinued from study. Notice 2 negative results from the same day do not equal confirmation.
- For a negative SARS-CoV2 confirmation, "Inconclusive" SARS-CoV2 result will not be considered as missing thus a "Negative" followed by a "Inconclusive" is NOT a confirmed negative PCR result.

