- All participants without a confirmed SARS-CoV2 negative result will be censored on the last day with available PCR test results.

GS-US-540-5823_SAP_v1.0_Final_Cohorts_1_to_8

ELECTRONIC SIGNATURES

Signed by	Meaning of Signature	Server Date (dd-MMM- yyyy hh:mm:ss)
PPD	Biostatistics eSigned	22-May-2023 11:23:50
PPD	Global Development Lead (GDL) eSigned	22-May-2023 18:13:26
PPD	Clinical Pharmacology eSigned	24-May-2023 14:33:01

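### Time to first confirmed negative PCR has two different censoring dates, in SAP Section 6.2.2 and Appendix 3 item 20, and no rule says which applies

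*SAP*

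**What the plan says.** Section 6.2.2 models time to first confirmed negative PCR by competing risks, separately for four sample types. Its rule begins "The competing event is death. Participants not not achieving a confirmed negative PCR at the last assessment" and ends by fixing the date: those without "a confirmed negative PCR at the last assessment will be censored on the day of the last clinical assessment".

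Appendix 3 item 20, headed with the same endpoint, gives another date: "All participants without a confirmed SARS-CoV2 negative result will be censored on the last day with available PCR test results".

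Appendix 3 item 17 collects the censoring rules for the competing-risk analyses. It covers improvement, recovery and discharge, for example "Time to discharge from hospital: Participants not discharge at the last assessment were censored on the day of the last clinical assessment", and does not mention PCR. No section ranks the main text against the appendix, and the term for the last clinical assessment is not defined.

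The schedule determines when the two dates can part:

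- PCR samples are due on Days 1, 3, 5, 7 and 10. PEWS and the Ordinal Scale are scored daily during dosing (Section 1.2).
- Tube aspirates are taken only from intubated participants (Section 1.2).
- Table 3-3, footnote: "If the participant is discharged prior to Day 10, the SARS-CoV-2 samples/swabs will be collected on the day of discharge". Later samples may be taken at "home or as an outpatient on the assigned days noted above, if feasible" (Section 1.2).
- Appendix 1, footnote b: "The following evaluations are to be completed on Days 2-10 or until discharge, whichever comes earlier".
- Day 30 in Appendix 1 includes "Complete or symptom-directed physical examination" and vital signs, but no PCR sample.

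**The concern.** A participant should count as at risk only while the event could be observed. For a PCR endpoint, that means until the last PCR result. The Section 6.2.2 rule is the one used there for the ordinal, PEWS and discharge endpoints, and it does not suit a laboratory outcome. Depending on how it is read, it either keeps children in the risk set after their last swab or discards PCR-positive time that was observed.

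Antiviral activity is a secondary objective (Section 1.1) and this is its time-to-event analysis, run by sample type in small cohorts. One or two children with discordant dates can move an estimate visibly, and the SAP as signed supports both versions.

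There is a second, smaller problem. Item 20 applies to all participants without a confirmed negative and makes no exception for deaths. Read literally, it would censor deaths that Section 6.2.2 treats as the competing event.

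**Working it through.** The SAP states no figure for this endpoint, so there is none to reproduce. The check has two parts: whether the two dates can differ under the SAP's own schedule, and whether the difference can change the estimate.

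**1. Can the dates differ?** Take a child discharged on Day 5 with a positive discharge-day swab.

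- *Reading (a): the last clinical assessment includes the Day 30 visit.* With no outpatient sample, Section 6.2.2 censors on Day 30 and item 20 on Day 5.
- *Reading (b): it means the last daily PEWS or ordinal score.* With no outpatient sample, both rules give Day 5. With positive outpatient swabs to Day 10, Section 6.2.2 gives Day 5 and item 20 gives Day 10.
- *Tube aspirates, either reading.* Sampling ends at extubation while scoring continues, so item 20 gives the earlier date.

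**2. Does it change the estimate?** All data below are assumed. The method is Aalen-Johansen cumulative incidence at Day 10, with events placed before censoring on tied days. Without deaths this is one minus the product of (at risk − events)/(at risk).

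Assume 12 children (the planned size of Cohorts 1-4), five confirmed by two consecutive negatives, first negative on Days 3, 5, 5, 7, 7 (used as the event date), and no deaths. If all seven others are followed to Day 10 or later, incidence is 5/12 = 0.417.

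| Unconfirmed children affected | Earlier censoring days | Rule with the earlier date | Rule with the later date |
|---|---|---|---|
| 1 | 5 | 1 − (11/12)(9/11)(6/8) = 0.438 | 0.417 |
| 2 | 5, 6 | 1 − (11/12)(9/11)(5/7) = 0.464 | 0.417 |
| 3 | 4, 5, 6 | 1 − (11/12)(8/10)(4/6) = 0.511 | 0.417 |

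- Under reading (a) without outpatient samples, item 20 has the earlier date and gives the higher figure.
- Under reading (b) with positive outpatient swabs to Day 10, Section 6.2.2 has the earlier date and gives the higher figure.
- Under reading (b) without outpatient samples, the rules agree.
- If one to three unconfirmed children have their last positive swab on Day 7, both rules give 0.417, because no event follows.

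*Tube aspirates.* Assume six intubated children, two confirmed (Days 3 and 5), and others scored to Day 10. Section 6.2.2 gives 2/6 = 0.333. If one child is extubated after a positive Day 3 aspirate, item 20 gives 1 − (5/6)(3/4) = 0.375. With two such children it gives 1 − (5/6)(2/3) = 0.444. Extubation may itself be informative, and neither rule corrects for that.

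*An extreme case.* Assume 12 children, six events (Days 3, 5, 7, 7, 10, 10), one death on Day 8, and all five others with discordant dates: last PCR on Days 3, 3, 5, 5, 7 and last clinical assessment on Day 10. Section 6.2.2 gives 6/12 = 0.50. Item 20, with death as the competing event, gives 1/12 + (11/12)(1/9) + (11/12)(8/9)(2/6) + (11/12)(8/9)(4/6)(2/3)(2/2) = 0.82.

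*Deaths under item 20 read literally.* Take the first cohort, with one unconfirmed child dying on Day 4 after a positive Day 3 swab. With death as the competing event, incidence is 1/12 + (10/12)(2/10) + (8/12)(2/8) = 5/12 = 0.417. With the death censored on Day 3 it is 1 − (11/12)(8/10)(6/8) = 0.450.

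**The case against.** The strongest reply is that item 20 obviously governs. It sits in the programming specifications, is headed with this endpoint and is the only rule written in PCR terms, while the Section 6.2.2 sentence looks carried over from the clinical endpoints, doubled word included. That is the natural guess, but the SAP does not say so. Section 6.2.2 also names this endpoint, and item 20 taken alone leaves the deaths question open.

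Reading (a) is also the weaker one. Scoring is daily during dosing, and where the SAP means to include the 30-day visit it uses another term, Last Study Date (Section 3.8.1). No PCR is scheduled after Day 10, so time at risk from Day 10 to Day 30 cannot change the estimate. Only the interval between the last swab and the last event matters. This stands. Reading (b) still leaves outpatient swabs and tube aspirates, where the rules part.

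It is fair, too, that little output depends on this. Counts of negative and confirmed-negative participants and the viral load summaries are unaffected. A negative last sample already counts as confirmed for those who completed or discontinued (Section 6.2.1), which limits who is censored. Section 6.2.2 promises no plot or median for this endpoint and names no main timepoint for it. The deaths point rests on a literal reading that Section 6.2.2 contradicts.

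A last fair point is that item 20 does not say whether samples excluded from the viral load analysis after additional COVID-19 treatment (Section 3.7) count as available results.

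**Conclusion.** The contradiction is real: one endpoint, two censoring dates, no precedence. Under the SAP's own sampling schedule the dates can differ in either direction, so the text needs correcting.

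The size in the real data cannot be known from the SAP. In the 12-child illustration, one to three affected children move Day 10 incidence by about 0.02 to 0.09. In the six-child aspirate illustration, one or two move it by about 0.04 to 0.11. The 0.50 against 0.82 case needs every unconfirmed survivor to be discordant. The difference is zero when the two dates coincide or no event falls between them.

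The consequence is limited to one descriptive secondary analysis. No formal testing is planned (Section 3.5), and no error rate or decision rule is touched. It should be fixed because it is cheap and the estimate is otherwise not determined by the plan.

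**What to change.** Replace the Section 6.2.2 censoring sentence, which also contains a doubled word, with:

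> *Participants who have no confirmed negative PCR result and have not died are censored on the last day with an available PCR result for that sample type; death is the competing event.*

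Use the same sample-type and death wording in Appendix 3 item 20, and add this endpoint to item 17. State in item 20 whether samples excluded under Section 3.7 count as available. As a minor conforming edit, align the Section 6.2.2 heading, which gives only the two-consecutive-negatives branch, with the two-branch definition in Section 6.2.1 and item 20.

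The cost is a few sentences and one heading, with no new data and no additional analysis. If the SAP is not reopened, Section 1 provides for changes after finalization to be documented in the CSR, and the chosen rule should be recorded there.

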6.3. Exploratory Efficacy Endpoints

6.3.1. Analysis of Exploratory Endpoints

CCI

CCI	

7. SAFETY ANALYSES

7.1. Adverse Events and Deaths

7.1.1. Adverse Event Dictionary

Clinical and laboratory AEs will be coded using the current version of MedDRA. System organ class, high-level group term (HLGT), high-level term (HLT), PT, and lower-level term (LLT) will be provided in the AE dataset.

7.1.2. Adverse Event Severity

The severity of AEs will be graded using the Division of AIDS (DAIDS) Table for Grading the Severity of Adult and Pediatric Adverse Events, Version 2.1 dated July 2017. For each episode, the highest grade attained should be reported as defined in the grading scale. The DAIDS scale is available at the following location:

https://rsc.niaid.nih.gov/sites/default/files/daidsgradingcorrectedv21.pdf

Adverse events are graded by the investigator as Grade 1, 2, 3, 4, or 5 according to toxicity criteria specified in the protocol. The severity grade of events for which the investigator did not record severity will be categorized as "missing" for tabular summaries and data listings. The missing category will be listed last in summary presentation.

